This study aims to validate the theranostic imaging biomarkers by assessing the change of maximum keratometry (K_{max}) after corneal cross-linking treatment (CXL). Based upon a systematic literature review, the study hypothesis is that CXL treatment can averagely flattening the K_{max} value by -1.05 D (SD: ± 0.80 D) at 1-year after CXL. To this scope, expecting a response rate of 50% of cases that will reach the threshold of -1.05 D of the K_{max} value, a sample size of 42 patients achieves 91% power to detect a difference of 0,2500 between the area under the ROC curve (AUC) under the null hypothesis of 0,6000 and an AUC under the alternative hypothesis of 0,8500 using a two-sided z-test at a significance level of 0,05000. Considering a $\leq 20\%$ drop-out rate (determined from

systematic literature review on controlled and open clinical studies on standard and epithelium-on CXL procedures), a number of 50 participants (25 per treatment protocol) is allowed to be enrolled in the study.

Products' description

The test articles to use in this study include two CE marked medical devices, such as the investigational one, herein the C4V CHROMO4VIS™ (CE1936) and the 0.22% riboflavin ophthalmic solution, herein the RitSight™ eye drop (CE0477), which must be applied onto the cornea before UV-A irradiation to protect the internal ocular structures from excessive UV-A light radiation.

The C4V CHROMO4VIS™ is a CE marked class IIb electronic UV-A medical device, which delivers ultraviolet light (365 nm wavelength) in a circular area onto the cornea. It is a portable system with articulating arm to allow movement of the system for alignment of the UV-A beam onto the patient's cornea. UV irradiance and irradiation time at the cornea are controlled by an onboard computer system. The medical device is equipped with the theranostic software (for research purpose only) that is the object of validation in this study. The RitSight™ is a CE marked sterile class IIa medical device consisting of a 0.22% riboflavin enriched solution for effective penetration of riboflavin into the corneal tissue to protect the inner ocular structures during UV-A irradiation.

Treatment

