Adequate records (*Case Report Forms*) will be maintained for the study including subject medical and surgical records, test reports, signed informed forms, and information about subject discontinuation. All original documentation will remain at the investigative sites. Study data that are generated electronically (e.g. corneal topography etc.) will be printed and retained in the study files. A unique identifier will be assigned by the Investigators to each trial subject to protect the subject's identity.

Dropouts/Lost-to-follow-up/withdrawal

Participants may drop out at any time during the study. Based on the scientific literature and considered the 1-year follow-up, a ≤20% dropout may be expected in the study. A total number of 50 participants is therefore allowed to be enrolled in the study.

Statistical Methods

Descriptive statistics will be used to summarize the data: numerical variables will be summarized as mean and standard deviation or median and interquartile range, respectively, according to the distribution of the data; categorical variables will be represented as frequencies and proportions. Student's t-test or Wilcoxon test will be applied to compare continuous variables, while Fisher's exact test or Chi-Squared test will be used to analyze categorical variables. ROC curve analysis will be used to evaluate cut-off values for the theranostic imaging biomarker scores in predicting the propensity of CXL treatment to flatten the K_{max} value at 12-months. The cut-off value for the biomarker scores will be determined by optimizing the Youden index. Moreover, sensitivity, specificity, proportion of correctly classified eyes and positive predictive value (PPV) positive predictive values (PPV) and false negative rate (FNR) and confidence intervals will be calculated. The study set a minimum threshold of 85% for the theranostic software module's accuracy and precision in predicting the propensity of CXL to halt disease progression (intended as more than 0.1 D K_{max} flattening) at 1 year in the study population (per protocol population).

Statistical significance will be set at 0.05. All the analysis will be performed using the statistical software R (latest version available).

Data Analysis

Data will be summarized using descriptive statistics and graphical presentations.

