Synopsis on disposition of participants

Sample size

By expecting a response rate of 50% of cases that will reach the threshold of -1.05 D of the K_{max} value, a sample size of 42 patients achieves 91% power to detect a difference of 0,25 between the area under the ROC curve (AUC) under the null hypothesis of 0,60 and an AUC under the alternative hypothesis of 0,85 using a two-sided z-test at a significance level of 0,05000. The data are continuous responses. Considering a $\leq 20\%$ drop-out rate (determined from systematic literature review on controlled and open clinical studies on standard and epithelium-on CXL procedures), a number of 50 participants (25 per treatment protocol) is allowed to be enrolled in the study.

Details on the methodology and process used to define the sample size of this clinical trial are described in Appendix 1 – Methodology for sample size calculation.

Statistical methodology

Descriptive statistics will be used to summarize the data: numerical variables will be summarized as mean and standard deviation or median and interquartile range, respectively, according to the distribution of the data; categorical variables will be represented as frequencies and proportions. Student's t-test or Wilcoxon test will be applied to compare continuous variables, while Fisher's exact test or Chi-Squared test will be used to analyze categorical variables. Bonferroni correction is applied to analysis of exploratory outcome measures of stratification groups. For all reported AEs, the data can be presented with events listed in order of decreasing frequency.

The optimal cut-off values in predicting the propensity of CXL treatment to flatten the Kmax value at 12-months was determined based upon the results of preclinical studies (data not disclosed to investigators to avoiding methodological study bias) and can be optimized with the Youden index. The accuracy and precision (95% CI) of the combined use of the theranostic imaging biomarkers to predict CXL treatment outcome will be determined by calculating the proportion of correctly classified eyes and the positive predictive value (PPV) respectively. The miss rate, which is the probability that a true positive is missed by the theranostic methodology, will be determined by calculating the false negative rate (FNR).

Statistical significance will be set at 0.05. All the analysis will be performed using the statistical software R (latest version available).

Population to be analysed

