The **Intent-to-Treat (ITT) Population** consists of all participants who were enrolled into the trial and performed at least 1 follow-up visit.

The **Per Protocol (PP) Population** will be a subset of the ITT population and will consists of all participants who participated and completed at least 66% of all the visits (i.e., 4 of 6 total visits) and the last visit 6 at day-360 and in whom there are no major protocol deviations.

Both populations will be agreed upon by Sponsor, Principal Investigator/Site of Investigation after the final subject visit and in advance of the database lock.

Ethical and Regulatory Issues

This study adheres with the ethical principles that have their origin in the Declaration of Helsinki (Seventh revision, 2013), the Convention of Oviedo, April, 4th 1997, and is consistent with GCP, including the ICH Guideline for good clinical practice E6, the Directive 2001/20/EC, the ISO 14155:2011, the Regulation (EU) 536/2014 of the European Parliament and of the Council of 16 April 2014, the Regulation (EU) 2017/745 of the European Parliament and of the Council of 5 April 2017, the Ministerial decree of the Italian Minister of Health of 2 August 2005, the Decree n.211 of 24 June 2003, the Ministerial Decree of 14 July 2009 and applicable regulatory requirements concerning human subject protection and other aspects of clinical investigations.

The study is conducted in strict compliance with the study protocol; any revision to study protocol must be discussed with and prepared by the Sponsor. The Investigator should not implement any deviation or change to the protocol without prior review and documented approval/favorable opinion from the Sponsor and IEC of an amendment. Any significant deviation must be documented in the CRF.

Good Clinical Practice (GCP) for Clinical trials

The Study will be conducted in accordance with the 13 principles of the rules of good clinical practice, as described below:

- 1) The study complies with the principles of the Declaration of Helsinki.
- 2) The expected benefits to participants justify the risks.
- 3) The rights, safety, and well-being of the participants to the trial are the most important considerations and prevail over those of science and society.
- 4) The available information about the investigational product are adequate to support the proposed clinical trial.

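### Fifty enrolled covers at most 16% loss: at the plan's own drop-out ceiling of 20%, 40 patients are evaluable, not the 42 behind the 91% power

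*Combined protocol and SAP*

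**What the plan says.** Under Statistical Considerations and Data Analysis, Sample size, the plan states that "a sample size of 42 patients achieves 91% power to detect a difference of 0,25". The quantity tested is the AUC, at 0.60 for the null and 0.85 for the alternative, with a z-test that is two-sided at 0.05. The outcome split behind this is given as "By expecting a response rate of 50% of cases that will reach the threshold of -1.05 D". The same paragraph takes into account a drop-out rate of at most 20%, attributed to a literature review, and ends with "a number of 50 participants (25 per treatment protocol) is allowed to be enrolled in the study". The Sample size paragraph of the Synopsis repeats these figures.

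The Synopsis paragraph on drop-outs, loss to follow-up and withdrawal makes the link explicit: a "dropout may be expected in the study. A total number of 50 participants is therefore allowed to be enrolled in the study".

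The Sample size section refers to Appendix 1 for the method. Appendix 1 reports literature values for the change in Kmax; it contains no drop-out figure, no inflation step and no AUC power formula.

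Under Population to be analysed, the per-protocol population must have completed at least 4 of 6 visits and the day-360 visit, and is limited to participants "in whom there are no major protocol deviations".

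**The concern.** An allowance for drop-out is meant to ensure that the number needed for the stated power remains when losses reach the allowed limit. Here 42 are needed, the limit is 20%, and 20% of 50 is 10, which leaves 40. The evaluable number, the enrolment figure and the drop-out ceiling therefore cannot all hold at the upper end of the range the plan sets itself.

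What is at stake is the accuracy of the stated power, not the viability of the trial. An ethics committee or regulator reading these paragraphs would take 91% as secured against 20% loss. No rule for replacing drop-outs and no lower working drop-out rate was found that would close the gap, and the enrolment sentence reads as a cap.

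**Working it through.** **Inputs** (Sample size sections and the Synopsis paragraph on drop-outs): 42 evaluable, 91% power, AUC 0.60 under the null and 0.85 under the alternative, two-sided 0.05, 50% responders (21 and 21 of 42), drop-out at most 20%, 50 enrolled.

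**1. The plan's power.** The formula is not named. For a one-sample z-test on the AUC with the null variance under the null and the alternative variance under the alternative,

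power = Φ((0.25 − 1.96 × SE₀) / SE₁).

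The Hanley-McNeil variance for m responders and n non-responders is

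[A(1 − A) + (m − 1)(Q₁ − A²) + (n − 1)(Q₂ − A²)] / (mn), with Q₁ = A/(2 − A) and Q₂ = 2A²/(1 + A).

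- At 21/21: SE₀ = 0.0880 and SE₁ = 0.0608, so power = Φ(1.276) = 89.9%.
- At 20/20: SE₀ = 0.0902 and SE₁ = 0.0624, so power = Φ(1.174) = 88.0%.

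The same calculation with other variances, and by simulation:

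| Method | 42 evaluable | 40 evaluable | Loss (points) |
|---|---|---|---|
| Hanley-McNeil | 89.9% | 88.0% | 1.9 |
| Obuchowski-McClish, simplified variance | 88.3% | 86.5% | 1.8 |
| Binormal, full covariance | 92.7% | 91.2% | 1.5 |
| Simulation (200,000 runs, binormal data, Obuchowski null variance) | 90.4% | 89.0% | 1.4 |

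The stated 91% for 42 lies within the 88 to 93% that these methods give, so it is reproduced to within the choice of formula.

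**2. The enrolment figure.**

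- Evaluable at 20% loss: 50 × (1 − 0.20) = 40.
- Largest loss that leaves 42: 1 − 42/50 = 0.16, that is 8 patients.
- Nine losses (9/50 = 18%) leave 41; ten (20%) leave 40.
- Enrolment that keeps 42 at 20% loss: 42 / 0.80 = 52.5, so 53, or 54 for equal groups of 27.
- Possible origin of 50: 42 × 1.20 = 50.4. This is an inference, because the documents do not show the step. Multiplying by 1 + d instead of dividing by 1 − d understates the number needed.

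**3. Rescaling the stated 91% to 40.** If both standard errors scale with 1/√n and r = SE₀/SE₁, then

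power at 40 = Φ((z(0.91) + 1.96r) × √(40/42) − 1.96r), with z(0.91) = 1.341 and √(40/42) = 0.976.

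This gives 89.6% for r = 1.0 and 89.2% for r = 1.5. If 91% was rounded from anywhere between 90.5% and 91.5%, the range is 88.7 to 90.2%.

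**The case against.** The strongest reply is that 20% is a ceiling, not an expected rate. The plan does not say in so many words that 42 remain at exactly 20% loss, and for any loss up to 16% its figures agree. This is correct, and it confines the problem to losses above 16% and up to 20%. It does not remove the problem: that range lies inside the stated allowance, and the Synopsis derives 50 from the allowance as a whole.

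A second reply is that the effect is negligible. The loss within any method (1.4 to 1.9 points) is smaller than the spread between methods at 42 (88.3 to 92.7%), the plan sets no minimum power that 40 would breach, and no design decision changes. This stands as a judgement of size. It argues for a correction in wording rather than in enrolment.

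A third is that a figure of about 89% at 40 cannot be fixed without knowing the formula, since the methods tried give 86.5 to 91.2%. This stands too: the final figure must come from the sponsor's own calculation.

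A fourth is that the 91% rests on a response threshold of −1.05 D, whereas the primary outcome uses flattening of more than 0.1 D and is judged by accuracy and precision of at least 85%. That is a separate and potentially larger matter. It does not make the drop-out arithmetic right.

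Finally, per-protocol exclusions might be thought to double-count drop-outs. In part they would, since a missing day-360 topography is listed as a major deviation and will often belong to a patient who has dropped out. No amount is therefore claimed for these exclusions.

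**Conclusion.** The concern holds. Enrolment of 50 protects the 42 evaluable patients behind the 91% only up to a 16% loss (8 patients). At the 20% ceiling 40 remain, two short, and power falls by 1.4 to 1.9 points, to about 89 to 90% if the stated 91% is taken as the starting point. These power figures assume the plan's own AUC values, significance level and 50% responders; the drop-out arithmetic assumes nothing beyond the stated 42, 50 and 20%.

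One point remains open. The AUC test is assigned to no analysis set, although the 85% accuracy and precision criterion is judged in the per-protocol population. If the AUC test is also run there, exclusions for major deviations not already counted as drop-out would lower the number further, by an amount the documents do not give. The error is certain and its effect is small; it should be corrected, but it does not threaten the trial.

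**What to change.** Add no patients. In the Sample size section of the Synopsis, the Synopsis paragraph on drop-outs, and Sample size under Statistical Considerations and Data Analysis, insert a sentence to this effect:

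> *Fifty enrolled allows for up to 16% loss (8 patients), leaving 42 evaluable and 91% power. At the 20% ceiling 40 are evaluable, with power of about 89% under the same assumptions.*

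The figure of about 89% is a placeholder. The sponsor should replace it with the value at 40 from the same formula and assumptions that gave 91%, and name that formula so that both figures can be reproduced.

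The cost is one sentence in each of three places and one rerun of the existing calculation. Design and analysis do not change; the stated power at 20% loss becomes about two points lower than 91%.

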- Measurement of **corneal endothelial cell density** (ECD) with specular microscopy will assess will assess changes of the ECD after treatment.
- **Slit lamp biomicroscopy** will assess integrity of the cornea and anterior segment of the eye.

Primary outcome measure

Validation of the Theranostic Imaging Biomarker [Time Frame: 12-months]

- Validation of the combined use of the theranostic imaging biomarkers. True positives, false positives, true negatives and false negatives were evaluated in order to determine the ability of the theranostic imaging biomarkers, including both the *riboflavin score* and *theranostic score*, to predict the propensity of CXL treatment in flattening the K_{max} value (D) by more than 0.1 D at 12 months postoperatively.

Theranostics: confirmation of the theranostic imaging biomarker will be provided at the end of treatment procedure. The theranostic data, which will be recorded during treatment procedure, will be exported to a computer for subsequent analysis with 12-months data.

The accuracy and precision (95% CI) of the combined use of the theranostic imaging biomarkers to predict CXL treatment outcome were determined by calculating the proportion of correctly classified eyes and the positive predictive value (PPV) respectively. The miss rate, which is the probability that a true positive is missed by the theranostic methodology, was determined by calculating the false negative rate (FNR).

The study sets a minimum threshold of 85% for the theranostic software module's accuracy and precision in predicting the propensity of CXL to halt disease progression (intended as more than 0.1 D Kmax flattening) at 1 year in the study population, who participated and completed at least 66% of all the visits (i.e., 4 of 6 total visits) and the last at 12 months (i.e., Per Protocol Population);

Secondary outcome measures

Efficacy [Time Frame: 12-months]

- Change of Maximum Keratometry index assessed by corneal topography at 12-months.

Corneal topography: measurement of maximum simulated keratometry (K_{max} , D) will be done by using Placido disk corneal topography. The investigator will record the K_{max} value at each visit and will fill the corresponding CRF. This test is performed to provide evidence of corneal curvature change after treatment.

Safety [Time Frame: 12-months]

- Change of Endothelial Cell Density assessed by specular microscopy at 12-months.

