- the CRF entries and other operating documents are filled with accuracy and completeness by Investigators.
- If CRFs have any entry error, omission, or illegibility, informing the investigator of it. The Sponsor shall ensure that appropriate corrections, additions, or deletions are made, dated, explained (if necessary), and initialed by the principal investigator.
- all adverse events are appropriately reported within the time periods required by GCP, the protocol, the IEC, the Sponsor, and the applicable regulatory requirement(s).
- if deviations from the protocol occur, communicating the applicable regulatory requirements to the investigator and taking appropriate action designed to prevent recurrence of the detected deviations.

Centralized monitoring will be performed by the Sponsor to review interim and final reports provided by the Principal Investigation/Site of Investigation. Review will include analyses of study data, including the following actions:

- to identify missing data, inconsistent data, data outliers, unexpected lack of variability and protocol deviations.
- to evaluate for systematic or significant errors in data collection and reporting at a site or across sites; or potential data manipulation or data integrity problems.
- to perform statistical analysis of study data.

Inspection of Records

The Principal Investigator/Site of Investigation will permit, at any working day, trial-related monitoring, audits, IEC review, and regulatory inspection(s) by providing direct access to all study records. In the event of an audit, the Principal Investigator/Site of Investigation agrees to allow the Sponsor, representatives of the sponsor, the Regulatory authorities to access to all study records.

The Principal Investigator/Site of Investigation should promptly notify the Sponsor of any audits scheduled by any regulatory authorities and promptly forward copies of any audit reports received to the sponsor.

Study Record Retention

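### The 85% criterion is judged on a Per Protocol set that has two definitions, drops eyes with complete primary data over missed interim visits, and is agreed without a masked review

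*Combined protocol and SAP*

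**What the plan says.** The Synopsis (Statistical Methods) sets an 85% minimum for the accuracy and precision of the theranostic software in predicting Kmax flattening of more than 0.1 D, "at 1 year in the study population (per protocol population". Accuracy is the proportion of eyes correctly classified and precision is the positive predictive value (PPV).

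The *Primary outcome measure* section repeats the threshold and describes the set as those who "completed at least 66% of all the visits (i.e., 4 of 6 total visits) and the last at 12 months (i.e., Per Protocol Population". It gives no other condition.

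The *Population to be analysed* section gives the same visit rule, that participants have "completed at least 66% of all the visits (i.e., 4 of 6 total visits", and then adds a condition: "and the last visit 6 at day-360 and in whom there are no major protocol deviations". The *List of major deviations/violation* has six items: inclusion criteria, exclusion criteria, signed consent, baseline topography, day-360 topography, and cross-linking not completed.

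On who decides and when: "Both populations will be agreed upon by Sponsor, Principal Investigator/Site of Investigation after the final subject visit". The sentence goes on to require that this be done before database lock.

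The *Statistical methodology* section withholds from investigators the preclinical data behind the cut-off. It does not extend this to the sponsor, and it allows the cut-off to be optimised with the Youden index. The ITT set is defined, but no analysis of the primary measure is assigned to it.

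**The concern.** The primary measure needs three things from each eye: the scores recorded at treatment, Kmax at baseline and Kmax at 12 months. A set built on other conditions can remove eyes that could be classified. It can also leave doubt about which eyes count when the two definitions disagree.

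The people who agree the set are also placed to know the results. With about 42 eyes and a fixed 85% bar, the status of a single eye can separate success from failure. The analysed set should therefore be unambiguous and settled by people who cannot see how each eye performed.

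**Working it through.** **1. The plan's own figure.** The *Sample size* section gives 91% power for 42 eyes, AUC 0.60 against 0.85, 50% positives, two-sided 5%. For a one-sample AUC z-test, power = Φ((0.25 − 1.96·SE0)/SE1), with 21 positive and 21 negative eyes. The Hanley-McNeil variance gives SE0 = 0.0880 and SE1 = 0.0608, so power = Φ((0.25 − 0.1724)/0.0608) = 89.9%. The Obuchowski-McClish binormal variance gives 92.7%. The stated 91% is reproduced to within 2 points. This power belongs to the AUC test, not to the 85% criterion.

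**2. The two definitions side by side.**

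| Condition | Primary outcome measure | Population to be analysed |
|---|---|---|
| At least 4 of 6 visits | yes | yes |
| 12-month visit | yes | yes |
| Free of major deviations | not stated | yes |

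The six listed deviations do not all matter equally:

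- Missing baseline or day-360 topography removes the outcome under either definition.
- If cross-linking is not completed, the efficacy index may not exist, because the operation sequence provides it with completion of the UV-A phase.
- The definitions therefore differ mainly on eligibility and consent failures.

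Eligibility is itself stated in two ways. The Synopsis accepts a change in manifest refraction as evidence of progression, and *Study Participants* omits it. A participant enrolled on refraction alone meets one text and not the other, so the passages must be reconciled.

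**3. The visit rule.** *Study Visits* counts six visits: baseline, days 7, 30, 90 and 180, and day 360. Treatment day is separate. An eye seen at baseline and day 360 has two visits and needs two more from visits 2 to 5 to reach 4/6 = 66.7%. An eye with complete primary data is excluded if it misses three or four of those interim visits. The rule is the same under both definitions.

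**4. How many eyes.** The documents give no missed-visit rate, so assume each interim visit is missed independently with probability m. Then P(at least 3 of 4 missed) = 4m³(1 − m) + m⁴.

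| m (assumed) | Probability | Expected, of 50 eyes |
|---|---|---|
| 5% | 0.05% | 0.02 |
| 10% | 0.37% | 0.2 |
| 20% | 2.7% | 1.4 |
| 30% | 8.4% | 4.2 |

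**5. Who can know what at sign-off.** Investigators record Kmax themselves at every visit. The operator is shown the index on the day of treatment, and the report goes into the patient record. Site interim reports carry an analysis of the primary measure at 6 months, and the sponsor reviews those reports. No masked review of the populations is described. That outcomes are known at sign-off is an inference from this data flow; the plan does not state it.

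**6. Sensitivity of the criterion, reading 85% as a point estimate.**

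- Accuracy: 36/42 = 85.7% passes and 35/42 = 83.3% fails. Removing one misclassified eye from the latter gives 35/41 = 85.4%, a pass.
- PPV, with 21 predicted positives as an illustration: 17/21 = 81.0% fails. Removing one false positive gives 17/20 = 85.0%, a pass.
- Suppose true accuracy is 80% with 42 eyes. The binomial chance of observing at least 85% is 23.8% with no exclusion (36 or more correct). It is 37.8% if one misclassified eye is removed (35 or more) and 53.1% if two are (34 or more). These last two figures are worst cases, because every excluded eye is a misclassified one.

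**The case against.** The best defence is that the set is more tightly controlled than it first appears. Agreement must come before database lock. Visit counts are objective and the major deviations are a fixed list. Knowing that an eye is misclassified takes the cut-off as well as the score and Kmax, and investigators are not given the preclinical cut-off data. The *Primary outcome measure* wording may be only a shorthand for the formal definition. Any fixed bar at this sample size turns on one eye, whichever set is used.

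Most of this stands, and it rules out several stronger readings that a reader might infer:

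- **That sponsor and investigators may drop eyes at discretion.** No passage grants that. What room there is comes from the conflicting definitions and eligibility texts, and from silence on whether a visit outside its window counts as completed.
- **That the sponsor alone runs the analysis.** The phrase "to perform statistical analysis of study data" sits under the sponsor's centralized monitoring. *Case Report Forms* refers to a statistician responsible for analysis during the study, and *Reports* has the final report sent to the sponsor for approval.
- **That the plan expects only 40 evaluable eyes.** Its dropout figure is an upper bound of 20%, so 50 × 0.80 = 40 is the worst case.
- **That the visit rule discards many eyes.** Step 4 does not support that.

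The defence does not remove the mismatch or the unneeded visit condition. Agreement before lock is also not masking, because scores and Kmax are visible as they are recorded and the sponsor is not covered by the cut-off restriction.

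**Conclusion.** The point holds in a limited form. The set that carries the 85% criterion has two definitions, differing by the major-deviation clause. Both exclude some eyes whose primary data are complete, on grounds that do not bear on the 12-month classification. Interim visits still matter for safety. The set is agreed by parties who may already know scores and outcomes, with no masked review described.

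The expected loss from the visit rule is small: about 0 to 4 of 50 eyes, resting on independent missed visits at assumed rates of 5% to 30%. The stated power is not in question. The consequence lies in how narrow the criterion is: one eye can move accuracy from 83.3% to 85.4%. That assumes 85% is a point estimate, since the plan does not say whether it applies to the estimate or to a confidence bound.

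A reader might go further and infer that the set is open to deliberate selection. The documents do not show that. The selective-exclusion figures are an upper limit on what could happen. The mismatch and the unmasked sign-off are reason enough to change the text.

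**What to change.** 1. Make the primary set all consented, treated study eyes with recorded scores, baseline Kmax and day-360 Kmax, whatever their attendance at visits 2 to 5.
2. Write one Per Protocol definition, identical in the Synopsis, *Primary outcome measure* and *Population to be analysed*, and tied to the *List of major deviations/violation*. Report it as a sensitivity analysis.
3. Have the list of analysed eyes signed before database lock by existing staff who have seen neither the scores nor the post-treatment Kmax. Signing before the score and Kmax files are merged would not be enough, because it does not mask anyone who has already seen both.

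The cost is protocol and SAP wording, one more run of the same table, and finding suitable masked staff for the sign-off. The downside is that a few eyes with eligibility deviations would enter the primary set; the Per Protocol table would show whether they matter.
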